## 4.2 Prior and Concomitant Therapy

Details on medications taken prior to randomization and any concomitant medications taken during the study must be recorded in the electronic case report form (eCRF). The data that will be collected are summarized in Table 4.

**Table 4: Categories of Concomitant Therapy**

Category	Details to be collected	Timelines
Antibiotics	Names, dose, date of administration	Allowed for prophylaxis if started >4 weeks before randomization
SSRIs	Names, dose, date of administration	Allowed if started or dose changed >8 weeks before randomization
CBT	Date of administration	Allowed if started >8 weeks before randomization and unchanged
NSAIDs	Names, dose, date of administration	Required as premedication only for infusions but not for treatment of PANS/PANDAS
Vaccines	Name, date of administration	Live virus vaccine allowed if administered >2 weeks before IMP and >3 months after last IMP infusion
Other concomitant medication	Name, date of administration	Within 28 days before randomization and during the study

### 4.2.1 Permitted Concomitant Therapy

Review of all concomitant medications and doses, and other interventions will be obtained at each study visit. Parents and patients will be advised to avoid the addition of new psychosocial or medical treatments such as e.g. probiotics, herbal remedies, over the counter medicine, supplements or antioxidants (e.g. N-acetyl cysteine – shown to decrease compulsions) during the double-blind phase, unless deemed medically necessary.

Application of a topical numbing agent is allowed prior to any intervention with a needle (blood draw or IMP administration).

Prescribed medication(s) and over the counter medications not listed as prohibited in Section 4.2.2 are allowed. In addition, permitted concomitant treatments include:

- Antibiotics for prophylaxis if started more than four weeks before randomization and the dose and frequency remain unchanged over the course of the study;
- CBT if started more than eight weeks before randomization and the frequency and intensity of treatment remains unchanged over the course of the study;
- Stimulants for ADHD if started more than four weeks before randomization and the dose and frequency remain unchanged over the course of the study;
- CBD/CBM-containing agents without THC if started more than eight weeks before randomization and the dose and frequency remain unchanged over the course of the study;
- NSAIDs as premedication to alleviate possible side effects of Panzyga infusions or as a short-term treatment (single doses over a few days) for the management of AEs, excluding the disease under study (PANS/PANDAS);
- SSRIs if started more than eight weeks before randomization and the dose remains unchanged over the course of the study;
- Prophylaxis for TEEs, if deemed necessary by the investigator, is allowed as a precautionary measure and should follow standard of care. Its use must be documented.

#### **4.2.2 Forbidden Concomitant Therapy**

Administration of forbidden concomitant therapy as listed below does not automatically trigger patient withdrawal; the patient will be moved from the per protocol analysis set to the intent-to-treat set (see Section 9.2.1). The following medications or therapies are not permitted during participation in this study:

- Immunosuppressive agents
- Antibiotics (unless given per protocol Section 4.2.1);
- CBT (unless applied per protocol Section 4.2.1);
- SSRIs (unless given as allowed per protocol Section 4.2.1);
- Mood stabilizers (e.g. Depakote, Lamotrigine, Lithium)
- Psychotropic medication for OCD, anxiety or tic disorder (e.g. alpha-2 agonists or antipsychotics), unless given in single doses prior to blood draws or infusions and after completion of psychiatric evaluations when dealing with agitated patients (e.g. one-time doses of Lorazepam);
- Stimulants for ADHD (unless given per protocol Section 4.2.1);
- THC-containing agents;
- CBD/CBM-containing agents without THC (unless applied given per protocol Section 4.2.1);
- NSAIDs (unless given per protocol Section 4.2.1);

- Immunoglobulin treatment other than Panzyga. Patients will be withdrawn from study treatment if IgG preparations other than Panzyga are administered;
- Other blood or plasma-derived products;
- Plasma exchange procedures, plasmapheresis;
- Known nephrotoxic medication;
- Live attenuated vaccines such as measles, rubella, mumps and varicella;
- Any experimental drug;
- Melatonin.

## 4.3 Withdrawal and Replacement of Patients

### 4.3.1 Premature Patient Withdrawal from the Study

Patients have the right to withdraw from the study at any time for any reason, without the need to justify their decision. The investigator also has the right to withdraw patients in case of AEs, poor compliance, or other reasons. Since an excessive rate of withdrawals can render the study non-interpretable, any unnecessary withdrawal of patients should be avoided.

For any withdrawals after study entry, the investigator will obtain all the required details and document the reason(s) for discontinuation in the eCRF. If the reason for withdrawal of a patient is an AE, the main specific event or laboratory test will be recorded in the eCRF, and the investigator will make thorough efforts to clearly document the outcome.

Patients who terminate the study prematurely are considered drop-outs. The investigator will schedule an Early Termination Visit, which is identical to the Week 18 Visit procedures.

Other reasons for premature termination of patients may be:

- Withdrawal of patient's consent.
- Pregnant and lactating patients will be immediately excluded from the study.
- Investigator's opinion that the patient may be severely harmed if he/she continues study participation, namely by the treatment and procedures requested by the study protocol.
- Patients do not comply with the study protocol.

### 4.3.2 Premature Patient Withdrawal from Study Treatment

Patients may be withdrawn from study treatment for the following reasons:

- Occurrence of a condition or disease that interferes with the study treatment or represents an exclusion criterion.
- Administration of IVIG other than Panzyga. All patients who received at least one dose of the study treatment should be followed up per protocol until the study end without administration of the study product.

- Occurrence of an AE or SAE, which in the opinion of the investigator, precludes further treatment with study medication (Section 7.3.2).

If a patient shows worsening of their symptoms based on CGI-Improvement ratings, they will be presented to the site PI for review and treatment planning. Patients for whom worsening continues at a minimal level ("5" or "mildly worse") for an extended period of six weeks (2 visits) or moderately or greater level ("6" or "7"; much worse or very much worse) since last visit (up to three weeks) will be considered for premature withdrawal from the study drug and administration of appropriate standard of care treatment unless clinical interventions using approved study procedures and/or mediations have a reasonable likelihood to improve symptoms. Patients who experience an emergency worsening of symptoms may at the discretion of the site clinician be withdrawn from the study drug at any time to obtain necessary standard of care treatment. In addition, patients who develop exclusionary criteria (e.g. bipolar disorder, suicide attempt) will be withdrawn from the study drug and will receive appropriate standard of care treatment. All patients withdrawn from the study drug prematurely will be asked to continue the study as planned with modification of the study schedule (e.g. IMP administration and related to it safety lab tests will be omitted). Details of concomitant medications and procedures administrated per standard of care will be captured in patient case reports.

The eCRF will contain an End of Treatment and an End of Study page. The End of Treatment page will record whether the patient will be followed up per protocol, to allow for correct patient status tracking and to provide the reason for the drug withdrawal.

#### **4.3.3 Patient Replacement Policy**

There will be no patient replacement in this study, but enrollment will continue until it is foreseeable that the number of patients required (according to the possible adaptations and the revised sample size determined at the interim analysis) for the evaluation of the primary endpoint will be achieved with the currently enrolled patients. 'Foreseeable' in this context means that the required number of evaluable patients will be achieved if the drop-out rate at the time remains unchanged for the remainder of the study.

### **4.4 Assignment of Patients to Treatment Sequences**

Patients will be identified by unique codes, including the site identification number and a sequence number assigned by an electronic system in strict order of enrollment. Randomization will be managed centrally by means of an interactive response technology (IRT) system and ensure balanced allocation of the patients to the two randomization arms within the defined strata. The fact that a patient has been randomized will be reported immediately and automatically to the investigator, the contract research organization (CRO) and the Sponsor.

Randomized patients are not permitted to re-enroll under any circumstance.

## 4.5 Protocol Deviations

Deviations from the protocol should be avoided. If deviations occur, the investigator should promptly inform the monitor and the implication of the deviation must be assessed and discussed. Any deviation must be documented, stating the reason and date and the action taken. The documentation must be kept in the investigator's study file and the Sponsor's study master file. A complete list of all critical, major and minor deviations will be compiled and regularly updated by the Project Manager and provided for preparation of the Clinical Study Report (CSR).

In case of any critical/major protocol deviation, the investigator and Octapharma will decide on the further participation of the patient in this study after having discussed all relevant aspects.

Examples of critical/major protocol deviations are:

- Patients who entered the study even though they did not satisfy the entry criteria.
- Patients who received the wrong treatment or incorrect dose (also see Section 5.4).
- Patients who received forbidden concomitant medication.

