6.2. Premature Termination of the Study

Both the Investigator and the Sponsor reserve the right to terminate the study at any time. In this event, any necessary procedure will be arranged on an individual study basis after review and consultation by both parties. In terminating the study, the Sponsor and the Investigator will ensure that adequate consideration is given to the protection of the patients' interests.

Regulatory authorities and IECs/IRBs should be informed in accordance with national regulations. Please refer to the protocol (sections 4.3.1 and 6.2.3) for further details on premature termination, in particular for the exact stopping criteria triggering temporary suspension/early termination of the entire study for an unacceptable increased venous TEE or acute renal failure risk in the Panzyga group compared to the placebo group.

In case the study is terminated prematurely, the SAP will be revised to address all issues arising from such special circumstances, and to confirm or redefine the scope of the analysis if necessary.

7. Analysis Populations

The following populations will be considered for the statistical analysis:

The **Intent-to-Treat set (ITT)** will include all randomized patients, regardless of whether the patient actually received study drug.

The **full analysis set (FAS)** will include all randomized patients who received at least part of one infusion of Panzyga or placebo

The **per-protocol set (PP)** consists of all patients of the FAS, excluding those with protocol deviations which may have an impact on the evaluation of the primary study outcome parameter(s). Only important protocol deviations with the potential to affect the study results substantially, or to invalidate the interpretation of the data obtained, will lead to exclusion of patients from the PP set; protocol deviations to be considered will include (but will not be limited to):

- Violations of the study entry criteria
- Withdrawal criteria that developed during the study
- Wrong treatment or incorrect dose
- Prohibited concomitant medication
- Incorrect completion of the CY-BOCS which affects the scoring

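### Protocol 4.3.1 and 4.5 allow a randomized child to be taken out of the study for non-compliance or a major deviation, so a Week 9 CY-BOCS that the intent-to-treat analysis needs can be lost by decision rather than by withdrawn consent

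*Protocol*

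**What the plan says.** **Ending participation in the study.** Protocol 4.3.1 states: "The investigator also has the right to withdraw patients in case of AEs, poor compliance, or other reasons". Its list of further reasons for premature termination includes "Patients do not comply with the study protocol", as an item separate from withdrawn consent. On status it says: "Patients who terminate the study prematurely are considered drop-outs". These patients have one Early Termination Visit, "which is identical to the Week 18 Visit procedures".

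Protocol 4.5 adds that after a critical or major deviation "the investigator and Octapharma will decide on the further participation of the patient in this study after having discussed all relevant aspects". Its examples are failure to meet the entry criteria, wrong treatment or dose, and forbidden concomitant medication.

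**Text that leans towards keeping the child under observation.**
- Protocol 4.3.1 asks that unnecessary withdrawals be avoided, without defining the term.
- Protocol 4.2.2 says forbidden therapy does not automatically lead to withdrawal, and that the patient moves from the per-protocol set to the intent-to-treat set.
- Protocol 4.3.2, on stopping study treatment, has two follow-up sentences: "All patients who received at least one dose of the study treatment should be followed up per protocol until the study end" and "All patients withdrawn from the study drug prematurely will be asked to continue the study as planned with modification of the study schedule".

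**The analysis.** The intent-to-treat set in SAP 7 "will include all randomized patients, regardless of whether the patient actually received study drug", and it is the main population for all efficacy analyses. Under SAP 8.2 and 8.3, missing Week 9 CY-BOCS scores are multiply imputed assuming missing at random. One sensitivity analysis substitutes the median change in the placebo group.

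**The concern.** An analysis of all randomized patients is only as good as the outcomes collected on them. Here the study team can end collection of the primary outcome for reasons unrelated to consent, and those reasons may be tied to how the child is doing. The medication forbidden in 4.2.2 includes psychotropic drugs for OCD or anxiety, SSRIs outside the allowed stable use, and immunosuppressive agents, all of which a worsening child might be given. Poor compliance may likewise follow from lack of benefit or from poor tolerance.

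If such a child leaves before Week 9, a score that could have been observed becomes an imputed one. The missing-at-random assumption is then asked to cover a gap that the protocol itself allowed. If the imputed values are too favourable or too unfavourable, and the arms are affected unequally, the treatment comparison shifts.

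**Working it through.** **1. The passages side by side**

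| Situation | Text that permits loss of the score | Text that points to keeping it |
|---|---|---|
| Poor compliance | 4.3.1: investigator may withdraw the child from the study | 4.3.1: avoid unnecessary withdrawal |
| Forbidden medication | 4.5: investigator and sponsor decide on further participation | 4.2.2: no automatic withdrawal; patient counted in the intent-to-treat set |
| Other major deviation, child already dosed | 4.5: same decision | 4.3.2: dosed patients followed to study end |
| Randomized, never dosed | 4.3.2: the follow-up-to-study-end sentence names only dosed patients | 4.3.2: the request to continue is not limited to dosed patients, but concerns those taken off study drug |
| Clinically important deterioration | 3.3.1: discontinued from the study, with termination procedures | 4.3.2: considered for stopping study drug, then asked to continue the study |

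Nothing in the right-hand column overrides the left. Rows three and five are direct tensions between sections, and the passages must be reconciled. The last row is raised only for its effect on data collection.

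**2. Does removal serve the analysis?** SAP 7 already excludes entry violations, wrong treatment or dose, and prohibited medication from the per-protocol set. These are the same kinds of deviation that 4.5 gives as examples. The per-protocol analysis therefore does not need the child to leave the study, and the intent-to-treat analysis loses an observation if the child does.

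**3. When it matters.** SAP 4.1 does not count drop-outs after Week 9 as withdrawals for the primary objective, so only removal before Week 9 affects the primary endpoint.

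**4. Possible size of bias.** The effect size and SD are blacked out, so there is no plan figure to reproduce. Let w be the share of an arm removed by decision before Week 9, and g the gap in CY-BOCS points between the true and the imputed change. Then:

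- shift in that arm's mean = w × g
- shift in the treatment difference = w₁g₁ − w₂g₂

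With w = 3–6% and g = 3–6 points (both assumed):

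- low end: 0.03 × 3 = 0.09 points
- high end: 0.06 × 6 = 0.36 points

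A second set of assumptions, with g = 2–6 points, gives 0.05 × 2 = 0.1 to 0.05 × 6 = 0.3 points at 5% removed, and 0.10 × 2 = 0.2 to 0.10 × 6 = 0.6 points at 10% removed. If both arms have the same w and g, the difference shifts by 0. If only one arm is affected, the difference shifts by the full arm figure, in a direction set by which arm it is and the sign of g.

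**5. Power.** The documents give 80% power and a 2.5% type 1 error rate (SAP 4.1) and 10% dropout (Study Outline). For a simple one-sided test the noncentrality is 1.960 + 0.842 = 2.802. At fixed enrollment and loss d it becomes 2.802 × √((1 − d)/0.90):

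| Loss d | Power |
|---|---|
| 10% | 80.0% |
| 12.5% | 78.9% |
| 15% | 77.7% |
| 20% | 75.2% |

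This ignores the adaptive design. It also overstates the loss, because Protocol 4.3.3 continues enrollment until the required evaluable number is foreseeable.

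**The case against.** The other side has a good deal of force.

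- **Removal is discretionary.** A reader might infer that children with deviations lose their Week 9 score as a rule. The documents do not say so: 4.5 calls for a case-by-case decision, and 4.2.2 expects users of forbidden therapy to be analysed in the intent-to-treat set. A rule of no automatic withdrawal is also compatible with a later decision to withdraw, so 4.2.2 and 4.5 do not strictly contradict each other.
- **Follow-up is not promised only to dosed children.** That reading rests on one sentence of 4.3.2. The other asks all patients taken off study drug to continue, without a dosing condition. It is still only a request, and it does not reach a child withdrawn from the study under 4.3.1 or 4.5.
- **The imputation may do better than feared.** SAP 4.1 has CY-BOCS collected every three weeks to Week 9, and the SAP version log records that covariates were added to the multiple imputation. If earlier scores are in the model, a child already deteriorating would not be imputed as an average completer. The model is not visible. Even a good model cannot see what happens after the last score.
- **Blinding should limit imbalance.** Similar removal in both arms largely cancels, and heavier removal of poorly doing placebo patients would work against Panzyga.
- **The never-dosed group may be small.** SAP 7 allows for the intent-to-treat and full analysis sets coinciding.
- **Hidden text.** Protocol 6.1, 9.2.1, 9.2.2 and 9.2.4, the flow charts and SAP 10.1 are blacked out. The Early Termination Visit may yield an off-schedule CY-BOCS, but no visible text uses it as the Week 9 value.

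These points narrow the concern. None of them closes the route by which an observable Week 9 score can be given up by decision.

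**Conclusion.** The concern holds in a limited form. Protocol 4.3.1 and 4.5 permit a randomized child's participation in the study, and not only in treatment, to end for non-compliance or a major deviation. No visible text secures the Week 9 CY-BOCS afterwards. This fits poorly with a primary analysis of all randomized patients. The single placebo-median analysis is one fixed scenario and cannot restore the lost observations.

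Neither the size nor the direction of any bias can be determined from the documents. The figure of about 0.1–0.4 points on a 40-point scale is an illustration for one arm, resting on assumed shares of 3–6% and gaps of 3–6 points. A reader might infer that the comparison is biased towards Panzyga, or that the 10% dropout allowance will be used up. The first does not follow, because the sign depends on which arm loses more and how those children fare. The second is largely answered by continued enrollment under 4.3.3. The change is worth making because it is cheap and preserves data that may be related to outcome.

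**What to change.** 1. In Protocol 4.3.1 and 4.5, separate stopping study drug from stopping study assessments. State that non-compliance and protocol deviations do not by themselves end scheduled assessments.
2. In 4.3.2, extend the follow-up commitment from patients with at least one dose to all randomized patients.
3. Seek the Week 9 CY-BOCS for every randomized child unless consent or assent is withdrawn, contact is lost, or a documented safety reason precludes assessment. The safety exception is needed because 4.3.1 recognises that study procedures may themselves harm a child.
4. Reconcile 3.3.1 with 4.3.2 on whether a deteriorating child leaves the study or stays for assessments off study drug, and 4.5 with 4.3.2 on dosed children with a major deviation. Which clinical rule applies is for the sponsor and investigators to settle.

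The cost is a wording amendment and a few extra assessment visits. Protocol 3.3.3 allows the CY-BOCS by video where an in-person interview is not possible, which eases some of these visits but does not make remote assessment the default.

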## 4.6 Subsequent Therapy

All patients who leave the study – be it prematurely or per-protocol (PP) – will continue PANS treatment as per the discretion of the investigator.

## 5 INVESTIGATIONAL MEDICINAL PRODUCT(S)

### 5.1 Characterization of Investigational Product(s)

Panzyga and placebo (0.9% w/v sodium chloride) will be referred to as Investigational Medicinal Products (IMP).

Panzyga is a 10% IVIG ready for IV administration. Panzyga is produced from a pool of at least 1000 donations of human fresh frozen plasma per batch. The large donor pool ensures that the product contains a broad range of antibodies directed against pathogens and foreign antigens, which is far more diverse than that of plasma from an individual donor. Donor plasma sampling, the manufacturing of the product and the measures to ensure the product's viral safety are subject to strict regulations laid down by regulatory authorities. Octapharma exclusively uses plasma that has been tested by nucleic acid testing techniques.

During the manufacturing process of Panzyga, significant viral reduction is obtained via a combination of [REDACTED] dedicated virus inactivation/removal steps. The composition with the most important ingredients and the biochemical characteristics are summarized in the IB [22].

For placebo, 0.9% w/v sodium chloride solution for intravenous infusion will be used. The placebo will be handled and monitored with the same diligence as Panzyga. Placebo and Panzyga should be stored and transported according to their respective product information. Conditions will be stated in the IMP Handling Manual.

